8.1.4 SRI Tumor Uptake in Documented Lesions

All patients are required to have [68Ga]-DOTA-TOC (e.g. Somakit-TOC[®]) PET/CT (or MRI when applicable based on target lesions) imaging or [68Ga]-DOTA-TATE PET/CT (or MRI when applicable based on target lesions) imaging (e.g. NETSPOT[®]) or Somatostatin Receptor scintigraphy (SRS) with [111In]-pentetreotide (Octreoscan[®] SPECT/CT) or SRS with [99mTc]-Tektrotyd or [64Cu]-DOTA-TATE PET/CT (or MRI when applicable based on target lesions) imaging performed within 3 months prior to the projected randomization date in the study (available exams older than 3 months need to be repeated to evaluate the patient's eligibility).

SRI imaging must be repeated before cross-over (after progression in the control arm), if the patient participates to the optional Treatment Extension Phase, and before the optional re-treatment (after progression in the Lutathera arm).

SRI tumor uptake in documented target lesions will be assessed locally to evaluate patient's eligibility before randomization, cross-over and re-treatment. Tumor uptake in all target lesions must be greater than the liver uptake.

Images will be also submitted to the central imaging center for a second review: there is no central 'real time' assessment of the SRI images, however the images should be submitted to the central imaging center possibly within 1 month. SRI images submission is not required for screening failure patients.

Lytic bone lesions, with an identifiable soft tissue component, evaluated by CT or MRI, can be considered as measurable lesions if the soft tissue component otherwise meets the definition of measurability according to RECIST 1.1 (in any case, blastic bone lesions are not measurable). Therefore, if the bone lesion has the characteristic as above, and SRI is positive, the patient may be enrolled.

If the primary tumor has been resected, tumor evaluations including SRI will be performed on metastases.

Operating details and quality certificates are specified in the Imaging Manual and Imaging Charter.

8.2 **Prior/Concomitant Medications**

All medications taken at the start of screening until the end of the Treatment Phase/optional Treatment Extension Phase/optional Re-treatment Phase, or early termination, are to be recorded. This includes prescription and over-the-counter medications taken during this time frame.

During the Follow up Phase, concomitant medications must be collected only if administered for related SAEs/AESI and/or for secondary hematological malignancies. In addition, further anti-tumor treatments administered after progression must be reported until the end of the Follow up Phase.

If any additional medication or procedure has been given for treatment of suspected or confirmed COVID-19 during the study, the site is requested to please enter them as a concomitant medication or procedure (e.g. intubation) and state/ select 'reason' to match the relevant Adverse Event reported when applicable.

Tests performed to diagnose symptoms of COVID-19 should be reported as Adverse Events only per Section 10.1.1 and not duplicated in Concomitant Medications/ Surgical and Medical Procedures or equivalent CRFs.

8.3 Efficacy Assessment

8.3.1 Progression Free Survival

The primary efficacy end-point is PFS as measured by objective tumor response, which is determined by RECIST criteria, Version 1.1 (Eisenhauer, et al., 2009). Tumor response will be assessed locally and centrally.

Triphasic CT imaging is the preferred modality over MRI for determining objective tumor response. Combined PET/CT may be used only if the CT is of similar diagnostic quality as a CT performed without PET, including the utilization of IV contrast media.

The baseline CT/MRI scan should be taken possibly on the same day of randomization or immediately before (within 1 week) to ensure that it reflects the disease status closely before the therapy start. The results of baseline CT/MRI must be assessed by the Investigator before randomization.

The tumor diameters of indicator lesions used for response assessment should be measured in the closest position to that used for the baseline CT or MRI assessment.

Restaging is scheduled at regular intervals in the two treatment arms (week 16 ± 1 , week 24 ± 1 and then every 12 ± 1 weeks) starting from the date of randomization (see Table 8-3, and Table 8-4). Every effort should be done to avoid differences between these timings for patients in the two arms. In case of delays, the reason of the delay has to be documented and the CT/MRI assessment has to be done as soon as possible.

If a CT/MRI scan is done on the same day of a Lutathera administration (e.g. in case of therapy postponement due to DMT or scheduling issues), the scan should be taken before the drug administration. When a CT/MRI assessment is >6 weeks earlier or later than the original schedule, the next reassessments have to be discussed and adjusted with the Medical Monitor of the study in a way to progressively come back to the original schedule.

It is recommended that for each patient identical acquisition and reconstruction protocols be used at all time-points. Central, blinded, real-time IRC (Independent Review Committee) assessment will be conducted for determining progressive disease. Changes from randomization date will be assessed at week 16 ± 1 , week 24 ± 1 and then every 12 ± 1 weeks until the PFS primary analysis End-Point has been reached, then until Week 72 after randomization, unless the patient progresses or dies.

Sponsor will notify all the Centers and their Ethic Committees as soon as the 99 PFS events have occurred.

Additional PFS/PFS2 data will be collected up to 3 years from the end of the Treatment Phase of the last patient (during the follow-up phase RECIST 1.1 assessment will be performed only locally every 6 months (\pm 1 month)).

Additional imaging assessments may be performed at any time during the study at the investigator's discretion to support the efficacy evaluations for a subject, as necessary. Clinical suspicion of disease progression at any time requires a physical examination and imaging assessments to be performed promptly rather than waiting for the next scheduled imaging assessment. These additional scans should be provided to the IRC for central assessment. If an off-schedule imaging assessment is performed because progression is suspected, subsequent imaging assessments should be performed in accordance with the original imaging schedule.

After progression and during the follow-up every effort must be made by the Investigator to collect additional information on further anti-tumor therapies and scan assessments outcome (RECIST 1.1 local evaluation) to evaluate the Time to Second Progression (PFS2) in the two study arms.

For progressive patients participating in cross-over or re-treatment, CT/MRI scans performed after the cross-over or re-treatment eligibility will follow the visits schedule counted from the 1st Lutathera dose.

For patients that are re-treated with Lutathera, a separate PFS analysis will be conducted during the re-treatment phase using the same definition as in Section 12.5.2 except that the baseline will be based on the tumor assessment which demonstrated progression thus allowing re-treatment with Lutathera. This PFS analysis during re-treatment will be descriptive only.

Operating details and quality certificates are specified in the Imaging Manual and Imaging Charter. See Section 8.8 for further details.

8.3.2 Objective Response Rate (ORR), Duration of Response (DOR), Time to Second Progression (PFS2)

Objective Response Rate (ORR) will be calculated as the rate of patients with a best overall response of partial response (PR) or complete response (CR). Response duration will be calculated from the time of initial response until documented tumor progression.

The Duration of Response (DOR) is defined as the time from initially meeting the criteria for response (CR or PR) until the time of progression by RECIST or death due to underlying disease. DOR will be reported descriptively for each group without comparison between groups.

As additional secondary exploratory end-point (local RECIST assessment), the Time to Second Progression (PFS2) will be assessed in the two study arms. PFS2 is defined as the time from randomization to the time of disease progression or death due to any cause (on any treatment) following the first episode of disease progression.

For patients that are re-treated with Lutathera, a separate analysis for ORR, DoR, and PFS2 will be conducted during the re-treatment phase using the same definition as in Section 12.5.2 for ORR and DoR, except that the new baseline will be based on the tumor assessment which demonstrated progression thus allowing re-treatment with Lutathera. The PFS2 definition is the same as that in Section 12.6.1. This ORR, DoR, and PFS2 analysis during re-treatment will be descriptive only.

It is recognized that the limitation of including cross-over and the lower scans frequency during follow-up will reduce the possibility to reach firm conclusions on PFS2.

After the first progression is confirmed centrally and the second progression is confirmed locally (i.e. after PFS2 event), the sites which do not routinely perform 6-monthly follow up CT/MRI scans for progressive GEP-NET patents can omit this examination at the subsequent patient's visits (no protocol deviation).

8.3.3 Overall Survival

Overall Survival (OS) will be calculated from the randomization date until the day of death due to any cause; OS will not be censored if a patient receives other anti-tumor treatments after study medication.

Overall Survival will also be separately estimated for patients that receive re-treatment with Lutathera. The definition for OS is the same to that in Section 12.5.2, and this analysis with re-treatment patients will be descriptive only.

Survival data will be analyzed at the time of the analysis of the primary end-point (PFS), and will continue to be assessed up to 4 years from the randomization of the last patient or 6 months after the last cross-over/re-treatment dose in the study, whichever occurs last.

8.4 Quality of Life

The impact of treatment on health related QoL will be assessed using the EORTC QLQ-G.I.NET21, EORTC QLQ-C30 and EQ-5D-L5 questionnaires, which will be filled in by the patient prior to know CT scan/MRI result. Changes from baseline will be assessed every 12 ± 1 week from the first treatment date until the end of treatment.

Forms in Country-specific languages will be provided by the Sponsor.

8.5 Safety and Tolerability

8.5.1 Adverse Events

All adverse events (AEs), whether or not spontaneously reported by the patient, will be recorded starting from the signing of the ICF until the end of the Treatment Phase/optional Treatment Extension Phase.

During the Follow up Phase only related SAEs and related AESI other than secondary hematological malignancies will be recorded. AESI of secondary hematological malignancies will be recorded during the whole study irrespective of causality. Definitions and reporting procedures are outlined in Section 10. An Independent Steering Committee Board will evaluate patient's safety throughout the study (Section 10.2). During the Follow-up Phase, concomitant medications must be collected in the eCRF if administered for related SAEs/AESI and/or for secondary hematological malignancies.

During the COVID-19 pandemic that limits or prevents on-site study visits, regular phone or virtual calls will occur for safety monitoring and discussion of the participant's health status until the participant can again visit the site.

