3.2 Treatment Phase

During the Treatment Phase, patients will be followed according to the assessments schedule in Table 8-3, and Table 8-4. Objective tumor response will be assessed at W16 \pm 1, W24 \pm 1 and then every 12 \pm 1 weeks from the randomization date, according to RECIST 1.1 criteria (central + local assessment up to first progression, then only local assessment).

Duration of the Treatment Phase:

• Before the PFS primary analysis:

The Treatment Phase is not fixed and the patients who are randomized should continue to receive the study treatments until progression or death (patients randomized in the Lutathera arm, will continue octreotide long-acting 30 mg injections after the completion of the 4 Lutathera treatments until progression or death; patients randomized in the octreotide long-acting arm will continue octreotide long-acting 60 mg injections until progression or death).

• After the PFS primary analysis:

The Treatment Phase becomes fixed and will stop at week 72 (patients randomized in the Lutathera arm, will continue octreotide long-acting 30 mg injections after the completion of the 4 Lutathera treatments until week 72 or earlier in case of progression or death; patients randomized in the octreotide long-acting arm will continue octreotide long-acting 60 mg injections until week 72 or earlier in case of progression or death).

In other words, before the PFS primary analysis (i.e. 99 evaluable and centrally confirmed disease progressions or death events), patients continue the Treatment Phase until progression; after the PFS primary analysis, the Treatment Phase duration is limited to 72 weeks.

At any time during the study (before or after the PFS primary analysis) any progressive patient (based on central imaging assessment) immediately ceases the Treatment Phase and proceeds to the Follow-up Phase (Table 8-3 and Table 8-4). If a patient discontinues Lutathera before centrally confirmed disease progression, the patient should be followed with tumor assessments as per initial CT/MRI schedule until centrally confirmed disease progression.

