- 5- CgA assessment being discontinued in Q3 2022 due to lab kits shortage in South Korea only
- 6- There is no central 'real time' assessment of the SRI images; the images should be submitted to the central imaging center possibly within 1 month.
- 7- SPECT/CT and WBPI post Lutathera injection requested in Germany only.
- 8- Only related SAEs & AESI will be collected during the Follow-up Phase, with the exception of AESI of secondary hematological malignancies which will be collected during the Follow-up Phase irrespective of causality (see Section 10.1.5 for AESI definition).
- 9- Only if a scan was not taken in the previous 12 weeks; if no post-baseline scan is available, a scan is needed at EOT.
- 10- For patients who entered the Lutathera re-treatment phase, since there are no procedures requiring in-person patient's attendance, the following visits can be performed by phone: Visits W32, 40, 44, 52, 56, 64 and 68 following Lutathera re-treatment (for Germany only: visits W56, 64 and 68). Post progression Re-Treatment Eligibility CT/MRI scan doesn't need to be repeated if performed within the previous 12 weeks. Both Re-treatment Eligibility SRI and CT/MRI scans need to be submitted to the central imaging center for a second review: there is no central 'real time' assessment of the Re-treatment Eligibility SRI uptake; however, the images should be submitted to the central imaging center possibly within 1 month.
- 11- Only if a scan was not taken in the previous 6 months.
- 12- During Follow-up Phase and at the EOS visit, concomitant medications must be collected only if administered for related SAEs/AESI and/or for secondary hematological malignancies. In addition, all new anticancer therapies administered must be collected till EOS.

Table 8-4. Assessment Schedule Octreotide Long-Acting 60 mg Arm.

Confidential

Visit Name	Scree ning	Tr	eatm	ent																	Furthe after 72	r Visits 2 weeks¹	EOT or early termination	Optional cross-over (4 Lutathera cycles) ²	3 years follow- up	EOS or early FUP terminati on
Weeks	-2 - 0	0	4	8	12	16	20	24	28	32	36	40	44	48	52	56	60	64	68	72	Every 4 weeks	Every 12 weeks	Within 4 weeks from last treatment		Every 6 months	Last FUP visit
Treatment		+	+	+	+	+	+	+	+	+	+	+	+	+	+	+	+	+	+	+	+	+		4x ♣↓		
Obtain informed consent	Х																							Complete all assessments in Table 8-3 from		
Demography	Х																							week -2 (except		
Inclusion/exclu sion criteria	х																							cancer diagnosis and		

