10.1 Definition of adverse events and reporting requirements

10.1.1 Adverse events

An adverse event (AE) is any untoward medical occurrence (e.g., any unfavorable and unintended sign [including abnormal laboratory findings], symptom or disease) in a subject or clinical investigation subject after providing written informed consent for participation in the study. Therefore, an AE may or may not be temporally or causally associated with the use of a medicinal (investigational) product.

The investigator has the responsibility for managing the safety of individual subject and identifying adverse events.

Abnormal laboratory values or test results occurring after informed consent constitute adverse events only if they induce clinical signs or symptoms, are considered clinically significant, require therapy (e.g., hematologic abnormality that requires transfusion or hematological stem cell support), or require changes in study medication(s).

The investigator has the responsibility for managing the safety of individual subject and identifying adverse events.

AAA qualified medical personnel will be readily available to advise on trial related medical questions or problems.

Adverse events that begin or worsen after informed consent must be recorded in the Adverse Events eCRF. Conditions that were already present at the time of informed consent must be recorded in the Medical History page of the subject's eCRF. Adverse event monitoring must be continued for at least 30 days (or 5 half-lives, whichever is longer) following the last dose of study treatment. Adverse events (including lab abnormalities that constitute AEs) must be described using a diagnosis whenever possible, rather than individual underlying signs and symptoms. When a clear diagnosis cannot be identified, each sign or symptom must be reported as a separate Adverse Event.

The occurrence of adverse events must be sought by non-directive questioning of the subject at each visit during the study. Adverse events also may be detected when they are volunteered by the subject during or between visits or through physical examination findings, laboratory test findings, or other assessments.

Adverse events must be recorded under the signs, symptoms, or diagnosis associated with them, accompanied by the following information (as far as possible) (if the event is serious refer to Section 10.1.2):

- 1. The Severity grade OR the Common Toxicity Criteria (CTC) AE grade.

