10.1.6 SAE reporting

To ensure subject safety, every SAE, regardless of causality, occurring after the subject has provided informed consent and until 30 days after the patient has stopped study treatment must be reported to AAA pharmacovigilance immediately, without undue delay and under no circumstances later than 24 hours following knowledge of its occurrence. Detailed instructions regarding the submission process and requirements are to be found in the investigator folder provided to each site.

All follow-up information for the SAE including information on complications, progression of the initial SAE and recurrent episodes must be reported as follow-up to the original episode immediately, without undue delay and under no circumstances later than within 24 hours of the investigator receiving the follow-up information. An SAE occurring at a different time interval or otherwise considered completely unrelated to a previously reported one must be reported separately as a new event.

Information about all AE/SAEs is collected and recorded on the SAE Report Form; all applicable sections of the form must be completed in order to provide a clinically thorough report. The investigator must assess and record the relationship of each AE/SAE to each specific study treatment (if there is more than one study treatment), complete the SAE Report Form in English, and submit the completed form under no circumstances later than 24 hours following knowledge to AAA pharmacovigilance.

Follow-up information is submitted in the same way as the original AE/SAE Report. Each reoccurrence, complication, or progression of the original event should be reported as a follow-up to that event regardless of when it occurs. The follow-up information should describe whether the event has resolved or continues, if and how it was treated, and whether the patient continued or withdrew from study participation.

If the SAE is not previously documented in the Investigator's Brochure or Package Insert (new occurrence) and is thought to be related to the study treatment, AAA pharmacovigilance associate may urgently require further information from the investigator for health authority

reporting. AAA may need to issue an Investigator Notification (IN) to inform all investigators involved in any study with the same study treatment that this SAE has been reported.

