12.5.3 Safety endpoints

For all safety analyses, the safety set will be used. All listings and tables will be presented by treatment group.

The frequency of adverse events and laboratory toxicities (scored according to CTCAE 5.0 grade or current version) will be presented.

All adverse events (AEs), whether or not spontaneously reported by the patient, will be recorded starting from the signing of the ICF until the end of the Treatment Phase.

Safety summaries (tables, figures) include only data from the on-treatment period with the exception of baseline data which will also be summarized where appropriate (e.g. change from baseline summaries). In addition, a separate summary for death including on treatment and post treatment deaths will be provided. In particular, summary tables for adverse events (AEs) will summarize only on-treatment events, with a start date during the on-treatment period (*treatment-emergent* AEs).

The on-treatment period lasts from the date of first administration of study treatment to 30 days after the date of the last actual administration of any study treatment.

The overall observation period will be divided into three mutually exclusive segments:

- pre-treatment period: from day of subject's informed consent to the day before first dose of study medication
- on-treatment period: from day of first dose of study medication to 30 days after last dose of study medication
- post-treatment period: starting at day 30+1 after last dose of study medication.
- There will be a dedicated presentation of safety for patients who cross-over.

Adverse events

All information obtained on adverse events will be displayed by treatment group and subject.

The number (and percentage) of subjects with treatment emergent adverse events (events started after the first dose of study medication or events present prior to start of double-blind treatment but increased in severity based on preferred term) will be summarized in the following ways:

- 1. by treatment, primary system organ class and preferred term.
- 2. by treatment, primary system organ class, preferred term and maximum severity.
- 3. by treatment, Standardized MedDRA Query (SMQ) and preferred term

Separate summaries will be provided for study medication related adverse events, death, serious adverse events, other significant adverse events leading to discontinuation and adverse events leading to dose adjustment.

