2.8.1 Adverse events (AEs)

All adverse events (AEs), whether or not spontaneously reported by the patient, will be recorded starting from the signing of the ICF until the end of the randomized period/cross-over period/re-treatment period. During the Follow up Phase, only related serious adverse events and adverse events of special interest will be recorded, except for secondary hematological malignancies which will be recorded irrespective of relationship to Lutathera, Octreotide, and amino acid. The data provides information regarding relatedness to Lutathera, Octreotide and amino acid.

AEs that started or worsened during the on-treatment period (including randomized treatment, cross-over and re-treatment periods as defined in [Section 2.1.1.10](#)) is defined as treatment-emergent AEs (TEAE). The primary AE summaries will focus on all treatment-emergent AEs in the randomized treatment period that started or worsened during the randomized treatment

period, defined as from date of first administration of study treatment to 30 days after the date of the last actual administration of any study treatment in the randomized period before cross-over or retreatment. However, selected AE summaries will also be generated for cross-over and re-treatment periods separately. All AEs collected in the eCRF page will be listed along with the information collected e.g., AE relationship to study drug, AE outcome etc. In addition, each AE record in the listings will be flagged for its study period based on the start date.

AEs will be summarized by number and percentage of subjects having at least one AE, having at least one AE in each primary system organ class (SOC) and for each preferred term (PT) using MedDRA coding. A subject with multiple occurrences of an AE will be counted only once in the respective AE category. A subject with multiple CTCAE grades for the same preferred term will be summarized under the maximum CTCAE grade recorded for the event. AE with missing CTCAE grade will be included in the 'All grades' column of the summary tables.

In AE summaries, the primary SOC will be presented alphabetically and the PT will be sorted within primary SOC in descending frequency. For randomized period AE summaries, the sort order for the PT will be based on their frequency in the investigational arm.

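### The adverse event recording rules conflict: one set stops all-cause recording when central progression ends the Treatment Phase, another runs to 30 days after the last dose, and only the second covers the analysed on-treatment window

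*Protocol*

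**What the plan says.** **Phase-based rule.** Protocol 8.5.1 has all adverse events "will be recorded starting from the signing of the ICF until the end of the Treatment Phase/optional Treatment Extension Phase". Section 12.5.3 gives the same kind of stop: events "will be recorded starting from the signing of the ICF until the end of the Treatment Phase". For the time after that, 8.5.1 says: "During the Follow up Phase only related SAEs and related AESI other than secondary hematological malignancies will be recorded". Secondary hematological malignancies are kept whatever the cause. Table 8-3 footnote 8 and Table 8-4 footnote 9 carry the same limit: "Only related SAEs & AESI will be collected during the Follow-up Phase". Section 10.1.5 applies the same phase split to AESI. SAP 2.8.1 repeats the restriction: "During the Follow up Phase, only related serious adverse events and adverse events of special interest will be recorded". The phase can end abruptly: under 3.2, "any progressive patient (based on central imaging assessment) immediately ceases the Treatment Phase and proceeds to the Follow-up Phase".

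**Dose-based rule.** Section 10.1.1 says: "Adverse event monitoring must be continued for at least 30 days (or 5 half-lives, whichever is longer) following the last dose of study treatment". Section 10.1.6 requires every SAE to be reported "regardless of causality, occurring after the subject has provided informed consent and until 30 days after the patient has stopped study treatment", and applies the related-only limit only after those 30 days.

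**Analysis window.** Protocol 12.5.3 and SAP 2.1.1.10 define the on-treatment period as running to 30 days after the last administration. The SAP cuts it at the day before the first extension-phase Lutathera dose if that comes sooner.

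**The concern.** The treatment-emergent summaries count every event with onset up to 30 days after the last dose. They can be complete only if every event in those days was recorded. A site that follows 8.5.1 and the table footnotes moves a patient to related-only recording at central progression, which can fall inside the 30 days. A site that follows section 10 keeps recording all causes. The same analysed days would then be filled under two different rules, depending on which section the site reads.

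Non-serious AEs are the most exposed, because the 24-hour reporting duty in 10.1.6 covers serious events only. Unrelated SAEs could reach the safety database under 10.1.6 and still be absent from the eCRF, which is what SAP 2.8.1 lists and summarizes. Dosing intervals differ between arms for part of the study, so any shortfall need not be equal in the two arms.

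Section 8.5.1 also omits the re-treatment phase, which the synopsis and SAP 2.8.1 include.

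**Working it through.** **Step 1: stopping points side by side**

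| Place | All-cause recording ends |
|---|---|
| Protocol 8.5.1 | End of Treatment Phase or Extension Phase |
| Protocol 12.5.3 (recording) | End of Treatment Phase |
| Table 8-3 fn 8, Table 8-4 fn 9 | Start of Follow-up Phase |
| Protocol 10.1.5 (AESI) | End of treatment phase |
| Protocol 10.1.1 | At least 30 days (or 5 half-lives, if longer) after last dose |
| Protocol 10.1.6 (SAEs) | 30 days after stopping treatment |
| Protocol 12.5.3 and SAP 2.1.1.10 (analysis) | Last dose + 30 days |

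Section 12.5.3 contains both the phase-based stop and the 30-day window. The SAP is also mixed. Its recording sentence in 2.8.1 ends with the treatment periods, which 2.1.1.10 extends to last dose + 30 days. Its related-only sentence applies from the Follow-up Phase, which 2.1.1.9 starts the day after the end-of-treatment date on the CRF. Both can apply to the same days.

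**Step 2: size of the gap under the phase-based rule**

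Let d be the days from last dose to the central progression call. Days of the analysed window under related-only recording = max(0, 30 − d).

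| d (days) | Gap (days) |
|---|---|
| 0 | 30 |
| 7 | 23 |
| 14 | 16 |
| 21 | 9 |
| 28 | 2 |
| 30 or more | 0 |

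The documents do not give d. Control injections are 4-weekly ± 3 days (6.1.1.2.1), so the longest planned interval is 28 + 3 = 31 days. Taking d from 0 to 31, the gap ranges from 0 to 30 days.

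**Step 3: other readings of when the phase ends**

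If the phase ends at an EOT visit on day 28, the gap is 30 − 28 = 2 days; on day 30 it is 0. An earlier visit leaves more. Section 8 asks for the visit as soon as possible after premature discontinuation, Tables 8-3/8-4 put it within 4 weeks of last treatment, and 9.2 puts it at 30 days.

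**Step 4: arms**

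During Lutathera cycles, dosing is 8-weekly, with octreotide preferably the day after. Then d can exceed 30 and the gap is 0. But Table 8-3 also schedules doses at weeks 16 and 24, the weeks of the first two scans. If that dose is given before the central read returns, d is short. After the cycles, octreotide is 4-weekly, as in the control arm. The gap may therefore differ by arm, but its direction and size are not fixed by the documents.

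**Step 5: truncation at cross-over**

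The SAP cut shortens the gap only if extension-phase Lutathera starts within 30 days of the last dose. Section 5.2.1 requires a 6-week washout from long-acting octreotide before cross-over Lutathera, which is 6 × 7 = 42 days. The cut should therefore rarely apply to control patients.

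Under the dose-based rule the gap is 0 throughout. The formula does not cover patients whose treatment continues after central progression at the investigator's request, because 8.8 keeps them on treatment-phase safety assessments.

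**The case against.** The strongest reply is that the protocol, read as a whole, already requires these events. Section 10.1.6 demands every SAE to day 30 and starts the related-only limit only afterwards. Section 10.1.1 continues AE monitoring for the same time, and 8.5.1 itself points to section 10. Section 9.1.1 lists adverse events and SAEs among the minimum data after treatment discontinuation, with no causality limit. The Adverse Events row in Tables 8-3/8-4 is marked at EOT separately from follow-up, and 9.2 schedules a 30-day safety visit. The synopsis, 3.4 and SAP 2.8.1 cover re-treatment.

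Much of this stands. A reader might infer that the protocol lets unrelated SAEs go unreported once central progression is called. It does not: 10.1.6 requires them to day 30.

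The conflict remains, though. The pointer in 8.5.1 is for definitions and reporting procedures, and section 10 is itself split, since 10.1.5 uses the phase-based rule for AESI. Section 9.1.1 collects its data per Tables 8-3/8-4, which leads back to the related-only footnotes. The EOT visit has three timings, and for cross-over patients the 28-day window is waived and the visit may be by phone. Whether the CRF end-of-treatment date is the progression decision or the visit is not defined.

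**Conclusion.** The rules contradict each other in the current text, and the phase-based one does not cover the analysed window. The consequence is conditional: at a site that follows 8.5.1, non-serious AEs, and unrelated SAEs in the eCRF, may be missing for up to max(0, 30 − d) days after central progression. The range is 0 to 30 days, or 0 to 2 days if the phase is taken to end at an EOT visit on day 28 to 30.

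Two further inferences should be resisted. One is that more than half of the window is lost. That needs a central read 7 to 14 days after an injection given in the week of the scan (a gap of 16 to 23 days), and the documents say only that review is real-time. Section 8 also warns that scans, timed from randomization, may not line up with visits timed from first treatment. The other is that most of the 99 patients with a PFS event are affected. PFS events include deaths, some patients progress more than 30 days after a dose, and no count can be derived. Nor do the documents show that event rates are in fact understated, only that they could be.

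This should be corrected: the wording change is cheap and it protects the safety comparison.

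**What to change.** Reconcile the synopsis, 8.5.1, 10.1.5, 12.5.3, the Table 8-3/8-4 footnotes and SAP 2.8.1 to one recording rule:

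- All AEs and SAEs, regardless of causality, are recorded in the eCRF until at least 30 days after the last dose, keeping the half-life clause of 10.1.1.
- The rule applies in each treatment period, including re-treatment, or until the first cross-over or re-treatment dose opens a new period.
- The related-only rule, with its exception for secondary hematological malignancies, starts after that.

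Make the EOT visit timing the same in section 8, 9.2 and Tables 8-3/8-4, and define the end-of-treatment date on the CRF.

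Recruitment is complete, but cross-over and re-treatment may start until 4 years after the last randomization, so the change still protects data to come. For data already collected, the SAP could tabulate by arm how many patients have an end-of-treatment date before the end of the analysed window.

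The cost is protocol and SAP wording, a site notice, and a few more weeks of AE entry for some patients.
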